Phenotypic Outcomes (AIM 1) and Biomarker DNA Age (AIM 2): We hypothesize that the VTEL high-intensity circuit exercise intervention will increase cardiorespiratory fitness and decrease sarcopenia and frailty (AIM 1) and decrease DNA Age (AIM 2). ANOVA models will be used with dependent variables of cardiorespiratory fitness (VO₂peak, 2-minute step test) and DNA Age (years). Logistic or multinomial models will be used with dependent variables of sarcopenia (present/not present) and frailty (robust/pre-frail/frail). Secondary analyses will be performed that use the individual components of composite outcome as their own dependent variable (e.g., lean mass and strength from sarcopenia). ANCOVA will be used to test for between group difference by time (pre/post exercise). Baseline performance and demographic and clinical characteristics will be included in models to assess and adjust for known potential confounding factors based on our experience with older HIV+ adults. We do not expect significant variability or effect from HIV-related factors (e.g., antiretroviral therapy, viral load) since we will use our previous established eligibility criteria. We do not anticipate needing to adjust for sex or race since each individual will function as their own control. Nutritional analyses of macro and micronutrients will be performed to measure any change during the study, and if present, will be tested for within group and between group effects. A similar approach will be applied to smoking exposure, which will be quantitated at baseline and follow-up testing. Treatment fidelity will be measured as percent of AEX time at target heart and entered in ANOVA models. For future planning, feasibility analyses will include calculation of rates for enrollment, retention, and attendance overall and by HIV group. Aggregate data will be collected on adverse events and reasons for lost to follow-up.

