On a weekly basis, each site PI is responsible for conducting safety reviews with staff and will be available by phone for urgent issues. When unavailable to staff, a designee is indicated. During exercise training, ongoing monitoring by the research coordinator is conducted prior to each exercise training session that includes vital signs and an established panel of safety questions and is documented on the exercise log CRF. The exercise physiologist will also monitor participant's heart rate and rating of perceived exertion (RPE) during the exercise training. If there is an issue, the participant will not exercise, and the site PI will be contacted and will evaluate the participant. A participant will be discontinued from the study and referred for medical care if any adverse event (AE), inter-current illness, or other medical condition or situation occurs such that continued participation in the study would not be in the best interest of the participant. Emergency procedures are in place should a participant need immediate medical attention during exercise training or testing.

Discontinuation Criteria:

- Lost to follow-up: Missing study visits and cannot be contacted
- Requested withdrawal: Participant requests to discontinue participation
- Death: Also an SAE that is reported to IRB
- Excluded: After study enrollment, development of a medical problem that meets exclusion criteria
- Completed: All study procedures have been performed after the exercise intervention

Minimal reporting requirements for the study are as follows:

AE/SAEs: All AEs must be graded for severity and relationship to the research procedure or intervention (see below) by a licensed clinician (i.e., physician, nurse, nurse practitioner, physician's assistant) but the relationship to the study can only be assessed by a clinician investigator familiar with the protocol. All SAEs will be reported to the site's local IRB as per VHA Handbook 1058.01 and local policy.

Severity of Event: All AEs will be assessed by the clinician using the following defined grading system:

- Mild: events require minimal or no treatment and do not interfere with the patient's daily activities.
- Moderate: events result in a low level of inconvenience or concern with the therapeutic measures. Moderate events may cause some interference with functioning.

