3 STUDY METHODS

3.1 Study Design

This study is a multi-site exercise intervention for Veterans receiving care at the Atlanta and Baltimore VAMCs that will randomize approximately 80 participants (40 per site) at these VAMCs, herein referred as enrollment sites. The intervention is 12-weeks of high-intensity functional circuit exercise performed 3 times weekly in a supervised group setting. Exercise training will be led by an exercise physiologist at the Salem VAMC (coordinating site) and broadcast to the enrollment sites. HIV-infected Veterans 50 years of age and older will be enrolled at the Atlanta and Baltimore VAMCs. Eligible participants will be randomized to exercise training (N=40) or control (N=40) groups. All participants will undergo baseline testing and follow up testing after 12 weeks at their respective enrollment site. Participants in the Control Group will be instructed to maintain their baseline sedentary lifestyle (as defined in eligibility criteria) during the 12-week intervention period. After follow-up testing is complete, participants in the control group will have the option of completing 12-week exercise training (delayed entry exercise) which will be a combined home and center-based exercise program. Pre-post exercise testing will be conducted in these participants to gauge individual progress and provide individual feedback that is a benefit of study participation, but these results will not be part of the randomized trial analyses.

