AEX, aerobic exercise; RT, resistance training

progress and any issues will be discussed on the monthly VTEL conferences with Drs. [name] (Salem), [name] (Baltimore), and [name] (Atlanta).

Adherence to Exercise Training Sessions: The intervention is designed as 12-weeks of exercise training performed 3 times weekly on Monday, Wednesday, and Friday for a total of 36 sessions. However, due to federal holidays, 36 sessions may not be feasible within 12 weeks and so time allowance will be made for 36 consecutive sessions to be performed with 100% adherence. Given that occasional missed exercise sessions will occur (usually due to travel in our experience), up to 3 additional exercise sessions will be offered to allow participants to reach 36 exercise training sessions. This provision minimizes the risk of muscle strain and exercise intolerance by allowing sufficient time to reestablish training progression and is a standard approach in progressive exercise training trials.

3.2.b Randomization

After baseline testing is complete, eligible participants will be randomized 1:1 to VTEL exercise or standard of care control groups. Randomization will occur in blocks of 2-10 participants at each site. An independent statistician will provide an allocation list for each site that will be managed by an individual without access to study data or contact with participants. The size of the block may vary by site and COVID safety practices. Block randomization is routinely used in smaller trials to ensure equal distribution between groups. In this application, it also serves to adjust the cohort size of each exercise group from a minimum of one participant to a maximum of five participants.

3.2.c Delayed Entry Exercise for Control Group

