5. Nutrition: There are minimal risks associated with the administration of the 24-hour diet recall. It is possible that some participants may feel uncomfortable discussing their diet.

6. Surveys: There are minimal risks associated with participants completing the surveys.

3.3.d Measures to Minimize Risk

The exclusion criteria have been developed for older HIV+ adults to minimize risk of adverse events. Exercise training will take place in rooms located within the Atlanta and Baltimore VAMCs near clinical areas and with specific safety procedures developed for VTEL exercise. A research staff member at the enrollment site will measure blood pressure before every exercise session and will remain in the room during the exercise class.

1. Exercise testing and training: Exercise testing will only be conducted after the participant is examined by a physician and the resting ECG and vital signs are obtained. A clinician (MD/NP) and exercise physiologist are present in the room with a defibrillator, emergency medications and resuscitation equipment during all testing. Exercise testing will be performed as per the guidelines of the American College of Sports Medicine. The ECG is continuously monitored. Specifically, a full 12-lead ECG, BP, and breathing are monitored during every minute of the test by personnel who are trained in cardiopulmonary resuscitation, exercise testing and emergency treatment of cardiac arrhythmias. The test will be stopped if electrocardiographic, heart rate, or BP abnormalities occur or if the participant has any symptoms of cardiovascular decompensation (e.g., chest pain, extreme dyspnea, dizziness or faintness, fatigue, pallor or cyanosis, cardiac arrhythmias including atrial fibrillation or flutter, frequent PVC's, second or third degree AV block or other intraventricular conduction defects, significant ST segment elevation or depression (> 2mm), SBP > 240 mmHg, DBP > 120 mmHg, or a decrease in SBP from the previous stage > 20 mmHg). Emergency medications are available should the participant need treatment. ECG, BP, and breathing are monitored for at least 6 minutes post exercise, or until the participant's heart rate and BP have returned to their pretest values. Disqualified participants will be referred to their physician for further evaluation. The clinician (MD/NP) and exercise physiologist are responsible for safety monitoring.

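### Safety questions are scheduled before up to 36 exercise sessions and no adverse-event query is stated for controls, so recorded counts can be expected to be higher under exercise at equal true rates

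*Combined protocol and SAP*

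**What the plan says.** Section 2.3.g (Data Safety Monitor Plan and Reporting) describes the routine safety contact with participants: "monitoring by the research coordinator is conducted prior to each exercise training session that includes vital signs and an established panel of safety questions". It is documented on the exercise log form. Section 3.2.a describes the training as "performed 3 times weekly on Monday, Wednesday, and Friday for a total of 36 sessions" and adds that "up to 3 additional exercise sessions will be offered to allow participants to reach 36 exercise training sessions".

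For the comparison group, section 3.1 says "Participants in the Control Group will be instructed to maintain their baseline sedentary lifestyle". The testing common to both arms is also in 3.1: "All participants will undergo baseline testing and follow up testing after 12 weeks at their respective enrollment site".

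Section 2.3.g defines, grades and classifies adverse events for all participants. It says that relationship to the intervention does not decide whether an event is reported, and that doubtful observations should be reported. It does not say how or when events are elicited from participants. On analysis, section 2.3.e says only: "Aggregate data will be collected on adverse events and reasons for lost to follow-up".

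**The concern.** How many events are recorded depends on how many occur and on how often somebody asks. A participant who is questioned every two or three days will report sore joints, colds and dizzy spells that a participant seen at the start and end of 12 weeks may forget or not think worth mentioning. Because the plan records events whether or not they are related to the intervention, these background events belong in the count.

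The control arm is the trial's only concurrent source for the background rate in sedentary older Veterans with HIV. If that rate is collected less completely than the exercise-arm rate, a by-arm count mixes harm with detection, and a pooled count mixes two levels of ascertainment. This cannot be repaired at analysis, because events that were never elicited are not in the database. It matters for a programme meant for wide dissemination, whose section 3.3.e concludes that benefits will exceed risks.

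**Working it through.** **1. Scheduled safety-question contacts in the randomised period**

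- Inputs: 3 sessions a week for 12 weeks (3.2.a); 40 per arm (3.1: "Eligible participants will be randomized to exercise training (N=40) or control (N=40) groups"); 30% expected attrition (3.3.a).
- Per exercise participant: 12 × 3 = 36, which reproduces the plan's figure. Make-up sessions serve to reach 36, so 36 is the maximum.
- Exercise arm at full attendance: 40 × 36 = 1,440. If 30% leave, 40 × (1 − 0.30) = 28, and completers alone give 28 × 36 = 1,008.
- Per control: none stated.

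**2. Do other contacts supply the missing query?**

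| Contact | Section | Arms | Described as adverse-event collection? |
|---|---|---|---|
| Physician examination, ECG and vital signs before treadmill testing ("Exercise testing will only be conducted after the participant is examined by a physician and the resting ECG and vital signs are obtained") | 3.3.d | Both | No |
| Three dietary recalls in each of the baseline and follow-up periods | 3.3.b | Both | No |
| Diet and weight monitoring, frequency not given | 3.3.b | Both | No |
| Weekly safety review by the site investigator | 2.3.g | Held with staff, not participants | Not a participant query |
| Weekly calls assessing tolerance | 3.2.c | Controls, in delayed entry only | Falls after the randomised comparison |

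Table 7, which summarises study procedures, lists no adverse-event procedure. Each shared contact gives some chance of capture, but none is a stated query.

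**3. Illustration of size**

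Let *p* be the true 12-week risk of having an event, the same in both arms, and *d* the probability that it is recorded. Expected participants with a recorded event = 40 × *p* × *d*. The recorded ratio is *d*(exercise) / *d*(control), because *p* cancels. The document gives neither *p* nor *d*; all values below are assumptions, with *d*(exercise) fixed at 0.9.

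| *d*(control) | Ratio | Counts, *p* = 0.20 | Counts, *p* = 0.30 | Counts, *p* = 0.50 |
|---|---|---|---|---|
| 0.9 | 0.9/0.9 = 1.00 | 7.2 vs 7.2 | 10.8 vs 10.8 | 18.0 vs 18.0 |
| 0.7 | 0.9/0.7 = 1.29 | 7.2 vs 5.6 | 10.8 vs 8.4 | 18.0 vs 14.0 |
| 0.5 | 0.9/0.5 = 1.80 | 7.2 vs 4.0 | 10.8 vs 6.0 | 18.0 vs 10.0 |
| 0.3 | 0.9/0.3 = 3.00 | 7.2 vs 2.4 | 10.8 vs 3.6 | 18.0 vs 6.0 |

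For example, at *p* = 0.30: 40 × 0.30 × 0.9 = 10.8 and 40 × 0.30 × 0.5 = 6.0.

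**4. Does relatedness grading remove the problem?**

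Section 2.3.g calls an event associated when it is close in time to a study procedure and has no other explanation. On a Monday-Wednesday-Friday schedule the gaps are 2, 2 and 3 days, so at full attendance almost any event during training follows a session by at most 3 days. Only the second condition then discriminates. Grading also applies only to events already recorded, so it cannot restore those missed in controls.

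**The case against.** The strongest reply is that nothing planned depends on this. Adverse events appear in no aim, no between-arm test or by-arm table is specified, and the sentence promising aggregate data directly follows the feasibility analyses. That stands: a reader might infer that a planned safety comparison is invalid, but the document contains no such comparison. What remains is the interpretation of whatever counts are reported.

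Second, the question panel is written as a check on whether someone should exercise that day. Its use as a source of adverse events is an inference, though a reasonable one: it sits in the safety plan and is documented on a case report form.

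Third, a reader might take the contrast as 36 prompts against zero. The zero means that none is stated. Controls do have other contacts, and the Manual of Operations, SOPs and case report forms, which hold the procedural detail, are not part of the document. A control schedule may exist there; if so, the protocol should state it.

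Fourth, a clinician investigator familiar with the protocol judges relatedness, so it goes too far to say that background events in trained participants will simply be labelled as harms of exercise. Grading helps with attribution but does not equalise capture.

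Finally, unequal contact is inherent in supervised exercise against a sedentary control, and the session checks serve safety. That is a reason to keep them and add a common source alongside.

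**Conclusion.** The concern holds as a weakness in data collection. As written, the plan prompts exercise participants before up to 36 sessions and states no adverse-event query for controls over the same 12 weeks. Recorded counts can therefore be expected to be higher under exercise at equal true rates. Mild and moderate events are most exposed; deaths and hospitalisations are less so, since they are likelier to come to notice in either arm.

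The size is not known. The ratios of 1.29 to 3.00 rest wholly on assumed capture probabilities, and the ratio is 1.00 if control capture is equally complete. A reader might infer that counts must differ, or differ by a particular factor; the document supports neither. The efficacy analyses are unaffected. The change is worth making because it is cheap and because the loss cannot be recovered after the data are collected.

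**What to change.** - At the existing 12-week visit, give both arms the same short adverse-event interview covering the whole period since randomisation.
- Use the clinical record, on the same terms in both arms, for serious events and for participants who miss the visit. Section 2.3.e already plans to obtain clinical data on dropouts who remain in VA care; this extends that use to adverse events. Dropouts who have left VA care would still be missed.
- In section 2.3.e, specify a by-arm adverse-event table built from these common sources, and report events found through session logs separately for the exercise arm.
- Leave the pre-session safety checks as they are.

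The cost is one short form at a visit that already takes place, a record review and one table. The downside is that 12-week recall will miss some minor events. Repeated questioning may also sharpen recall in exercisers, so the imbalance is reduced but may not be fully removed.

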3 STUDY METHODS

3.1 Study Design

This study is a multi-site exercise intervention for Veterans receiving care at the Atlanta and Baltimore VAMCs that will randomize approximately 80 participants (40 per site) at these VAMCs, herein referred as enrollment sites. The intervention is 12-weeks of high-intensity functional circuit exercise performed 3 times weekly in a supervised group setting. Exercise training will be led by an exercise physiologist at the Salem VAMC (coordinating site) and broadcast to the enrollment sites. HIV-infected Veterans 50 years of age and older will be enrolled at the Atlanta and Baltimore VAMCs. Eligible participants will be randomized to exercise training (N=40) or control (N=40) groups. All participants will undergo baseline testing and follow up testing after 12 weeks at their respective enrollment site. Participants in the Control Group will be instructed to maintain their baseline sedentary lifestyle (as defined in eligibility criteria) during the 12-week intervention period. After follow-up testing is complete, participants in the control group will have the option of completing 12-week exercise training (delayed entry exercise) which will be a combined home and center-based exercise program. Pre-post exercise testing will be conducted in these participants to gauge individual progress and provide individual feedback that is a benefit of study participation, but these results will not be part of the randomized trial analyses.

3.2 Coordinating Center at the Salem VAMC (Research Activities Conducted at SVAMC)

3.2.a Exercise Intervention: VTEL Exercise Training

Exercise Training Description

The exercise physiologist located at the SVAMC will be responsible for conduct of all exercise training under the supervision of the PI. Exercise training will be delivered by VTEL broadcast from the Salem VAMC to participants at the Atlanta VAMC and Baltimore VAMC. In the event that the Salem EP is not available to deliver the training, the exercise training can be delivered by another experienced EP through a telehealth platform. Research staff at the Atlanta and Baltimore VAMCs will be in the room with the participant to help with heart rate monitors and portable exercise equipment, and in the event of an emergency. Rooms will be equipped with steps, hand and ankle weights, dumbbells, chairs, and bands. No stationary exercise equipment will be used in either aerobic (AEX) or resistance training (RT). The intervention consists of high-intensity circuit exercise training performed 3 times weekly for 12 weeks in a group setting. Circuit training is an exercise modality consisting of a series of exercises at different stations.

Functional Circuit Training Details: The group exercise training sessions will be performed 3 times weekly and last approximately an hour, including warm up (8-10 min.), functional circuit training (48 min.), and cool-down/stretching (8-10 min.). Our clinical program, Tele-Gerofit, supports the feasibility of this design in a small area where each station is not defined necessarily by an area but by available equipment.⁴⁹ Each exercise circuit will consist of one AEX station and three RT stations with minimal rest between stations. The AEX will be performed for three minutes. Each RT station will include 1-3 sets of a strength exercise that is completed within 3 minutes (min). The total exercise time per circuit is 12 minutes (3 min. AEX + 9 min. RT (3 x 3 min.)). Heart rate is monitored during the entire circuit with targets set for AEX and RT that is analogous to high-intensity interval training. Details are provided under exercise intensity. Specific exercises to be used for AEX and RT for each circuit are summarized in Table 4. Progression of intensity is performed by increasing the size of the steps (AEX) and number of repetitions and weight of dumbbells or hand/ankle weights (RT). In the first week, only 1-2 RT exercise set will be performed as the participant becomes acclimated to the exercises for a total of 24-36 minutes (6-9 mins/circuit). Then participants will advance to three sets per RT exercise for a total of 48 minutes of high-intensity circuit training.

Exercise Intensity: To ensure that *AEX intensity* is met, participants will wear Polar HR monitors (Polar, Lake Success NY) with alarm limits set by the exercise physiologist and programmed into the watch by enrollment site staff. The AEX protocol will follow exercise interventions protocols that have been successful in older HIV+ Veterans. Participants will initially train at 50% heart rate reserve (HRR), increasing target HR by 5-10% weekly until 70-80% HRR is reached. Based on our work to date, three minutes of AEX per circuit is feasible. *Resistance training (RT)* progression will also be based on our prior experience with center-based progressive high-intensity RT in HIV+ adults. This protocol involves initial weight lifting of 50-60% 1-RM in two sets of 8 repetitions with progression to 12 repetitions. Then training weight is increased by an amount (~10%) that causes the muscle group to fatigue/fail after eight repetitions. However, functional RT exercises utilize multiple muscle groups, unlike traditional RT. Therefore, we will use the number of repetitions for specific functional RT exercises as the target, based on thresholds set by Rikli and Jones. The use of hand and ankle weights and multiple muscle engagement will help provide higher intensity RT. Strength exercises will be performed until muscle fatigue at three stations of the circuit with each strength exercise performed quickly.

Treatment Fidelity: The exercise physiologist will maintain a training log for each exercise session for each participant. The log includes the type of each RT exercise and number of sets, the type and duration of each AEX exercise, and any special participant feedback or concern. The heart rate will be measured and recorded continuously using a chest-strap heart rate monitor (Polar Electro Inc., Lake Success, NY) and downloaded by the

enrollment site staff at their site. The exercise physiologist will compile and review weekly HR data on the Salem VAMC shared folder to document AEX duration and intensity. The exercise physiologist will meet weekly with [name] to ensure interim training targets are met for each participant. In addition,

Table 4. Circuit Exercises by Modality

Circuit	AEX (Target HR)	RT (8-12 reps)
1	Step Ups	Bicep curls
		Chest Press
		Lateral Shoulder Raise
2	Shadow Boxing	Romanian Dead Lift
		Side Bends
		Calf Raises
3	Step Ups	Squat
		Reverse Wood Chop
		Bent Over Row
4	Lateral Side Steps	Lateral Band Walk
		Triceps Extension
		Wide Pull

AEX, aerobic exercise; RT, resistance training

progress and any issues will be discussed on the monthly VTEL conferences with Drs. [name] (Salem), [name] (Baltimore), and [name] (Atlanta).

Adherence to Exercise Training Sessions: The intervention is designed as 12-weeks of exercise training performed 3 times weekly on Monday, Wednesday, and Friday for a total of 36 sessions. However, due to federal holidays, 36 sessions may not be feasible within 12 weeks and so time allowance will be made for 36 consecutive sessions to be performed with 100% adherence. Given that occasional missed exercise sessions will occur (usually due to travel in our experience), up to 3 additional exercise sessions will be offered to allow participants to reach 36 exercise training sessions. This provision minimizes the risk of muscle strain and exercise intolerance by allowing sufficient time to reestablish training progression and is a standard approach in progressive exercise training trials.

3.2.b Randomization

After baseline testing is complete, eligible participants will be randomized 1:1 to VTEL exercise or standard of care control groups. Randomization will occur in blocks of 2-10 participants at each site. An independent statistician will provide an allocation list for each site that will be managed by an individual without access to study data or contact with participants. The size of the block may vary by site and COVID safety practices. Block randomization is routinely used in smaller trials to ensure equal distribution between groups. In this application, it also serves to adjust the cohort size of each exercise group from a minimum of one participant to a maximum of five participants.

3.2.c Delayed Entry Exercise for Control Group

Since the start of the study, participants randomized to the standard of care control group have had the option of entering an exercise training program after completion of 12-week follow-up testing, extending their participation time. This delayed entry exercise program, beyond the RCT design, has been provided so that the potential benefits of exercise are available to all participants despite initial randomization allocation. In the interest of ensuring that all participants may receive exercise toward the end of the award, the delayed entry exercise program will be changed from an identical one in the VTEL intervention arm to a hybrid home and center-based program. Since this may affect willingness to participate, the change in protocol will be implemented at the initial screening and recruitment of a cohort, not active participants.

The new delayed entry exercise program leverages advances in commercial physical activity trackers which now accurately measure wrist-based heart rate and are validated in older adults.⁵⁰ Delayed entry exercise will consist of 12-weeks of home-based exercise that is an individualized exercise prescription based on maximum heart rate, like the VTEL exercise group. However, a Garmin wrist device (Garmin Vivosmart 5, Garmin International, Inc. Olathe, KS, USA) will be used rather than a Polar heart rate band for heart rate monitoring. A Garmin Connect account will be generated by study staff which will include a “dummy” email that is not accessible to the participant and has no PHI/PII. The participant’s heart rate data from treadmill testing will be entered into each Garmin Connect account to define moderate intensity and vigorous intensity based on the same heart rate zones as used by the Polar monitors. Participants will be asked to wear the Garmin device continuously during waking hours, placing it on the charger each night at bedtime. Wear-time adherence will be assessed by a participant Garmin paper log which will include non-wear time and technical issues. This Garmin-based exercise program will include phone feedback at least weekly and in-person support group sessions at least monthly. These sessions will be conducted by an exercise physiologist who will adjust and progress the participant’s exercise prescription based on individualized weekly targets and personal tolerance.

Research coordinators at the Atlanta and Baltimore sites will conduct an initial orientation visit for each participant to setup the Garmin device and link it with the Garmin Connect app on their personal cell phone. One device will be given to each participant as an incentive for participation in the delayed entry exercise group. Coordinators will help install the Garmin Connect app on the participant's personal phone to ensure location tracking is off and no PII (e.g., personal email) is used. Education with written material will be provided on specific exercise (e.g., walking, jumping jacks) and activities (e.g., mowing lawn) which do not require specialized equipment and are classified as either moderate intensity or vigorous intensity.⁵¹ For the first 4 weeks participants only moderate intensity exercise/activity will be provided. Target duration will begin with 15 minutes of daily moderate intensity activity and will be progressed 10-15% weekly or as tolerated by the participant with a 1-month goal of 150 minutes of moderate physical activity per week ACSM Physical activity Guidelines for Americans.⁸ After 4 weeks, participants will be instructed to increase intensity to include vigorous exercise/physical activity with the 12-week goal of at least 75 minutes of vigorous intensity activity per week. The participant will be instructed to synch the Garmin wrist device with the phone app prior to the weekly call with the exercise physiologist, who will then review minutes in each intensity level on the Garmin Connect web site. This weekly call will last 30-60 minutes and will be used to assess tolerance, provide motivational feedback based on behavioral change techniques and make adjustments to progression of exercise in duration and intensity. This combination of activity trackers and feedback sessions has been effective in sedentary older adults.⁵²⁻⁵⁵ A monthly in-person group session will be held at each site which includes participants in the delayed entry control group from the same enrollment cohort. An exercise physiologist will lead a group discussion on challenges and incentives of exercising for the purpose of encouraging peer-support, which has been observed in the VTEL sessions. These sessions will occur after weeks 4, 8, and 12 of the exercise training period. At the 12-week in-person session participants will meet with the local site research coordinator who will uninstall the Garmin Connect app on the participant's phone and reset the Garmin device. Participants will be provided instructions on how to establish a personal Garmin Connect account which cannot be accessed by research staff for use after the end of the study.
